#### **7.4.3. Pregnancy**

- Details of all pregnancies in female subjects will be collected after the start of dosing and until the follow-up contact.

- If a pregnancy is reported then the investigator should inform GSK within 2 weeks of learning of the pregnancy and should follow the procedures outlined in Section 12.4.. Appendix 4.

Note: Subjects randomized in the epoetin beta pegol group should be advised to inform the investigator if they discover pregnancy in 7 weeks after the last dose of study treatment.

#### **7.4.4. Medical Device Incidents (Including Malfunctions)**

The medical devices are being provided for use in this study. The investigator is responsible for the detection and documentation of events meeting the definitions of incident or malfunction that occur during the study with such devices.

The definition of a Medical Device Incident can be found in Appendix 8 (Section 12.8.)

NOTE: Incidents fulfilling the definition of an AE/SAE will also follow the processes outlined in Section 7.4.1. and Appendix 6 (Section 12.6.) of the Protocol.

##### **7.4.4.1. Time Period for Detecting Medical Device Incidents**

- Medical device incidents or malfunctions of the device that result in an incident will be detected, documented and reported during all periods of the study in which the medical devices are available for use.
- If the investigator learns of any incident at any time after a subject has been discharged from the study, and such incident is reasonably related to a medical device provided for the study, the investigator will promptly notify GSK.

NOTE: The method of documenting Medical Device Incidents is provided in Appendix 8 (Section 12.8.).

##### **7.4.4.2. Follow-up of Medical Device Incidents**

- All medical device incidents involving an AE, will be followed until resolution of the event, until the condition stabilizes, until the condition is otherwise explained, or until the subject is lost to follow-up (as defined in Section 5.4.). This applies to all subjects, including those withdrawn prematurely.
- The investigator is responsible for ensuring that follow-up includes any supplemental investigations as may be indicated to elucidate as completely as practical the nature and/or causality of the incident.
- New or updated information will be recorded on the originally completed form "Medical Device Incident Report Form" with all changes signed and dated by the investigator.

##### **7.4.4.3. Prompt Reporting of Medical Device Incidents to GSK**

- Medical device incidents will be reported to GSK within 24 hours once the investigator determines that the event meets the protocol definition of a medical device incident.
- Facsimile transmission of the "Medical Device Incident Report Form" is the preferred method to transmit this information to the SAE contact information.
- The same individual will be the contact for receipt of medical device reports and SAEs.
- In the absence of facsimile equipment, notification by telephone is acceptable for incidents, with a copy of the "Medical Device Incident Report Form" sent by overnight mail.

**7.4.4.4. Regulatory Reporting Requirements for Medical Device Incidents**

- The investigator, or responsible person will comply with the applicable local regulatory requirements relating to the reporting of incidents to the IRB/IEC.

**7.4.5. Vital Signs/Height/Weight**

Systolic and diastolic blood pressure and pulse rate will be measured in sitting or semi-supine position after at least 5 minutes rest prior to clinical examination at each visit blood pressure and pulse rate.

One reading of blood pressure and pulse rate will be taken and recorded in the source document and the CRF. Height and weight will be measured at screening visit only.

**7.4.6. Electrocardiogram (ECG)**

12-lead ECGs will be recorded in supine position. The heart rate, PR, QRS, and QT (pre-corrected) intervals will be measured. QTcB should be calculated by machine or manually by designated staff at each site. The investigator determines whether the ECG data is assessable or not.

At the Day 1 visit when an ECG is performed, two additional ECGs are required if initial ECG indicates prolonged QTc using the automated or manually calculated QTcB value. The average QTcB value of all three ECGs will be used to determine eligibility.

QTc exclusion criteria can be found in Section [5.2](#). Refer to SRM for further details.

**7.4.7. Clinical Laboratory Assessments**

All study-required laboratory assessments will be performed by a central laboratory with the exception of HemoCue Hgb. The results of each HemoCue Hgb must be entered into the subject's eCRF. Details are provided in the SRM.

All laboratory assessments, as defined in [Table 15](#), must be conducted in accordance with the Laboratory Manual and Protocol Time and Events Schedule. Laboratory requisition forms must be completed and samples must be clearly labeled with the subject number, protocol number, site/center number, and visit date. Details for the preparation and shipment of samples will be provided by the central laboratory. Reference ranges for all parameters will be provided to the site by the central laboratory. Details of blood sampling (including the volume of blood to be collected) as well as procedures for processing, storage, and shipment of samples are provided in the SRM.

PK assessment of GSK1278863 is outlined in Section [7.5](#).

**Table 15      Laboratory Assessments**

Laboratory assessment	Parameter		
Hematology	Platelet count	RBC indices:	WBC count with Differential
	RBC count	MCV	Neutrophils
	Reticulocyte count	MCH	Lymphocytes
	Hemoglobin	MCHC	Monocytes
	Hematocrit	RDW	Eosinophils
			Basophils
Clinical chemistry	Sodium	AST	Bicarbonate
	Potassium	ALT	Inorganic phosphate
	Chloride	Creatinine	Glucose
	Calcium (total and albumin-corrected)	Total bilirubin	Direct/indirect bilirubin
	Albumin	Urea nitrogen	
	Total cholesterol	HDL cholesterol	LDL cholesterol
Iron parameters	Serum iron	Serum ferritin	Serum transferrin
	TIBC	UIBC	TSAT
	Hepcidin		
Urinalysis (ND subjects only)	Urine albumin	Urine creatinine	Urine albumin/creatinine ratio
Other laboratory tests	FSH 	Estradiol 	iPTH
	eGFR 	hCG (serum or urine) 	

1. Measured in female subjects only to determine the menopausal status (see Section 5.1.)
2. Calculated from serum creatinine using the Japanese Society of Nephrology-Chronic Kidney Disease Initiatives (JSN-CKDI) formula
3. Performed in females of childbearing potential: serum pregnancy test will be performed if urine pregnancy test is not feasible.

If additional non-protocol specified laboratory assessments are performed at the institution's local laboratory and result in a change in subject management or are considered clinically significant by the investigator (or subinvestigator) (e.g., SAE or AE or dose modification), the results must be recorded in the eCRF.

Refer to the SPM for appropriate processing and handling of samples to avoid duplicate and/or additional blood draws.

All laboratory tests with values that are considered clinically significantly abnormal during participation in the study should be repeated until the values return to normal or baseline. If such values do not return to normal within a period judged reasonable by the investigator (or subinvestigator), the etiology should be identified and the Sponsor notified.

#### 7.4.8. Ophthalmology

Ophthalmology exams will be performed by a study-designated ophthalmology specialist. Each assessment will include a comprehensive eye exam with at least the following components: measurement of best corrected visual acuity, intraocular pressure, an anterior aqueous chamber exam, and a fundoscopic exam. These exams will be used for assessment of ocular adverse events. Assessment results will be captured on worksheets which will be transferred to the eCRF. Additional details on the process for completing these assessments are provided in the SRM.

## 7.5. Pharmacokinetics

Blood samples for PK analysis of GSK1278863 will be collected from only subjects in the GSK1278863 group as outlined in [Table 14](#), and the date and time of the last two study medication doses taken prior to blood sampling as well as the date and time of sampling must be recorded in the eCRF.

Blood PK analysis will be performed under the control of GSK Platform Technologies and Science-Drug Metabolism and Pharmacokinetics (PTS-DMPK)/Scinovo and GSK-Japan Bioanalysis, the details of which will be included in the SPM. Concentrations of parent GSK1278863 will be determined in blood samples using the currently approved analytical methodology. Raw data will be archived at the bioanalytical site.

Procedures for processing, storage, and shipment of samples are provided in the SRM.

## 7.6. Genetics

A blood sample will be collected for genetic analysis from consenting subjects. This sample can be collected on Day 1 once written informed consent has been obtained. Information regarding genetic research is included in Section [12.7](#). Appendix 7.

## 7.7. Patient Reported Outcome (PRO)

The patient reported outcome (PRO) [e.g., symptoms, severity, health-related QOL (HR-QoL), health status] will be assessed using several rating scales.

All questionnaires used in this study have been translated into Japanese and validated.

Specific instructions on how the subject is to complete the scales and the process for data entry are provided in the SPM.

### 7.7.1. SF-36

The SF-36 acute version is a general health status questionnaire designed to elucidate the patient's perception of his/her health on several domains, including physical functioning, role physical, bodily pain, vitality, social functioning, role emotional, mental health, and general health over the past seven days. The questionnaire contains 36 Likert type questions that ask the patient to recall how he/she felt during the past seven days.

### 7.7.2. EuroQol Health Utility Index (EQ-5D-5L)/EQ Visual Analogue Scale (EQ-VAS)

The EQ-5D-5L is intended to measure the general health status and health utility. The EQ-5D-5L consists of 2 concepts: self-reported health status consisting of five dimensions (mobility, self-care, usual activities, pain/discomfort, anxiety/depression) each of which can take one of five responses and self-rated health status on a visual analog scale (VAS), a thermometer-like line.

## 8. DATA MANAGEMENT

- For this study subject data will be entered into GSK defined CRFs, transmitted electronically to GSK or designee and combined with data provided from other sources in a validated data system.
- Management of clinical data will be performed in accordance with applicable GSK standards and data cleaning procedures to ensure the integrity of the data, e.g., removing errors and inconsistencies in the data.
- Adverse events and concomitant medications terms will be coded using MedDRA (Medical Dictionary for Regulatory Activities) and an internal validated medication dictionary, GSKDrug.
- CRFs (including queries and audit trails) will be retained by GSK, and copies will be sent to the investigator to maintain as the investigator copy. Subject initials will not be collected or transmitted to GSK according to GSK policy.

## 9. STATISTICAL CONSIDERATIONS AND DATA ANALYSES

A detailed description of any planned analyses will be documented in a RAP..Any deviations from the analyses described in the protocol will be documented in the RAP or the final study report.

### 9.1. Hypotheses

The primary objective of the study is to demonstrate the non-inferiority of GSK1278863 to epoetin beta pegol based on mean Hgb during the primary efficacy evaluation period (Weeks 40 to 52) in ND subjects (Cohort 1).

As a preliminary assessment, it will be confirmed whether the mean Hgb during the primary efficacy evaluation period in GSK1278863 group would be in target range (11.0-13.0 g/dL) at first. And then the following non-inferioritystatistical hypotheses are to be tested at a one-sided significance level of 2.5% (i.e. two-sided significance level of 5%):

- $H_0$ : Treatment difference in mean Hgb during the primary efficacy evaluation period is -1.0 g/dL or less.
- $H_1$ : Treatment difference in mean Hgb during the primary efficacy evaluation period is greater than -1.0 g/dL.

Only when the primary endpoint achieves non-inferiority, statistical testing will progress to the principal secondary endpoint with a focus on superiority according to the step-down procedure. More specifically, the superiority of GSK1278863 to epoetin beta pegol in terms of target Hgb control in ND subjects is to be demonstrated at a two-sided significance level of 5% by testing the following statistical hypotheses:

- $H_0$ : The proportion of subjects whose mean Hgb during the primary efficacy evaluation period is within the target range (11.0-13.0 g/dL) is equal between the treatment groups.
- $H_1$ : The proportion of subjects whose mean Hgb during the primary efficacy evaluation period is within the target range (11.0-13.0 g/dL) is different between the treatment groups.

No hypothesis will be tested in PD subjects (Cohort 2).

## 9.2. Sample Size Considerations

### 9.2.1. Sample Size Assumptions

Assuming a non-inferiority margin of -1.0 g/dL, a treatment difference of 0.0 g/dL, and a standard deviation of 1.5 g/dL for mean Hgb during the primary efficacy evaluation period in ND subjects, two-sample t-test has at least 99% power at a one-sided significance level of 2.5% (i.e. two-sided significance level of 5%) with a sample size of 100 subjects per group. Assuming a dropout rate of approximately 25%, 135 subjects will be randomized to each group. Given the results from previous non-inferiority studies of similar drugs (darbepoetin alfa, epoetin beta pegol, and peginesatide), the non-inferiority margin of -1.0 g/dL is set. Since an increase of 1.0 g/dL indicates improvement in anemia according to the guidelines for renal anemia in Japan, the non-inferiority margin of -1.0 g/dL may be the clinically acceptable largest difference in renal anemia.

While the present study is designed to ensure long-term safety data from 100 ND subjects, and the primary hypothesis test has at least 99% power to estimate the efficacy very precisely, non-inferiority can be statistically demonstrated with a minimum between-group difference of -0.582 g/dL.

For PD subjects, the sample size is based on the feasibility. Assuming a sample size of 38 subjects and a standard deviation of 1.5 g/dL, the half width of the 95% CI for mean Hgb during the primary efficacy evaluation period is 0.493 g/dL.

### 9.2.2. Sample Size Sensitivity

The power is shown according to treatment difference and standard deviation in [Table 16](#).

**Table 16 Power Sensitivity (100 Subjects Evaluated, Noninferiority Margin of -1.0, One-Sided Significance Level of 2.5%)**

Treatment difference	Standard deviation		
	1.25	1.5	1.75
0	100.0%	99.7%	98.0%
-0.1	99.9%	98.8%	95.1%
-0.2	99.5%	96.4%	89.6%
-0.3	97.6%	90.7%	80.4%

### 9.2.3. Sample Size Re-estimation or Adjustment

No sample size re-estimation is planned for this study.

## 9.3. Data Analysis Considerations

### 9.3.1. Analysis Populations

- All Screening Population

The All Screening Population consists of all subjects who are given subject number and whose data are collected, including demographics at screening.

- Intent-to-Treat (ITT) Population (All randomized population)

The Intention-To-Treat Population consists of all subjects who are given randomization number regardless of whether they actually receive study treatment. Subjects will be analyzed according to randomized treatment. This population will be the primary population for an assessment of non-inferiority.

- modified ITT (mITT) Population

The mITT Population consists of all ITT subjects who have at least one Hgb measurement during the efficacy evaluation period. Subjects will be analyzed according to randomized treatment. This population will be the primary population for an assessment of superiority.

- Per-Protocol (PP) Population

The PP Population consists of all mITT subjects who are not major protocol violators. Subjects will be analyzed according to the treatment received. Details will be defined in the RAP. This population will be used for efficacy sensitivity analyses.

- Safety Population

The Safety Population consists of all ITT subjects who receive at least one dose of study treatment. Subjects will be analyzed according to the treatment received. This population will be used for safety analyses.

- PK Population

The PK Population consists of all GSK1278863-treated subjects from whom PK samples are collected and analyzed.

Additional populations may be defined in the RAP.

### **9.3.2. Interim Analysis**

No interim analysis is planned.

### **9.3.3. Adjustment for Multiplicity**

Adjustment for multiplicity will be applied to maintain an overall type I error rate of 5%. After a preliminary assessment, the primary endpoint will be evaluated to demonstrate the non-inferiority at a one-sided significance level of 2.5% (i.e. two-sided significance level of 5%). Only when the primary endpoint achieves non-inferiority, statistical testing will progress to the principal secondary endpoint with a focus on superiority. Since the process will follow step-down manner, a multiplicity adjustment for significance level of 5% will not be needed according to a closed test procedure.

Other secondary endpoints, which will be evaluated on a complementary or exploratory basis, will be compared at a significance level of 5% without multiplicity adjustment.

Since Cohort 2 is a single-arm cohort, no testing will be performed to evaluate the efficacy in PD subjects.

### **9.4.2. Principal Secondary Efficacy Analysis**

The principal secondary endpoint, which is the proportion of subjects whose mean Hgb during the primary efficacy evaluation period is within the target range will be analyzed to demonstrate the superiority of GSK1278863 to epoetin beta pegol in ND subjects.

In the mITT Population, a logistic regression model including treatment group, baseline Hgb, and current ESA therapy (presence or absence) as covariates will be used to estimate the point estimate and 95% CI for the odds ratio (GSK1278863/epoetin beta pegol). This analysis will be performed to demonstrate the superiority at a two-sided significance level of 5%, conditional on the primary endpoint achieving noninferiority. Superiority will be established if the lower limit of the 95% CI for odds ratio is greater than 1.0.

### **9.4.3. Other Secondary Efficacy Analyses**

Among the secondary efficacy endpoints, the time (%) in Hgb target range during the primary efficacy evaluation period, proportion of subjects who have an Hgb increase of more than 2 g/dL over any 4 weeks, and changes in iron metabolism parameters (ferritin, TSAT, hepcidin, serum iron, and TIBC), the point estimates and 95% CIs for the treatment difference (or odds ratio) in ND subjects will be calculated. Other secondary efficacy and exploratory endpoints will be summarized by each treatment group.

For PD subjects, the efficacy endpoints will be descriptively summarized.

#### **9.4.4. Safety Analyses**

In principle, safety data will be summarized by each cohort and each treatment group in the Safety Population.

##### **9.4.4.1. Exposure**

Exposure information will be listed for all subjects. The duration of treatment (number of days) and cumulative dose will be tabulated. In addition, distribution of the dose level at each assessment visit and final dosing visit will be tabulated. Frequency of dose adjustment and duration of treatment interruption due to Hgb >13 g/dL will be summarized.

##### **9.4.4.2. Adverse Events**

All AEs will be categorized by the MedDRA system organ class and preferred term to tabulate the number and incidence. All AEs, SAEs, AEs leading to discontinuation of study treatment, and AEs of special interest will be summarized separately. Similar summary will be provided for study treatment-related AEs.

##### **9.4.4.3. Other Safety Parameters**

For laboratory tests, vital signs and ECG, parameters and/or changes from baseline will be summarized using summary statistics at each assessment visit. The number and percentage of subjects with values of the potential clinical importance values will be tabulated. The criteria for the potential clinical importance will be described in the RAP. For lipid parameters (total cholesterol, LDL cholesterol, and HDL cholesterol), percent changes will also be tabulated. The number (%) of subjects who have any change in anti-hypertensive medications (type and/or dose) due to increased blood pressure will be tabulated.

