### **Open-label**

If the study is conducted as a double-blind study, it is necessary to not only administer GSK1278863 orally (once daily) or epoetin beta pegol subcutaneously (once every 2 or 4 weeks), but also administer the matching placebo subcutaneously or orally. It will be more stressful for subjects and complicate treatment procedures to use both active drug and matching placebo for two drugs with different routes and intervals of administration for the purpose of maintaining the blind, and make dose adjustments for individual subjects according to the change in Hgb over time. Accordingly, this study is designed as an open-label study rather than a double-blind study, which seems infeasible. Since Hgb used for efficacy evaluation is an objective measure, and dose adjustments for study medication will be made according to the prespecified Hgb-based dose adjustment method in both GSK1278863 and epoetin beta pegol groups, it is unlikely that the open-label design will create any bias in the primary evaluation.

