## 6.5. Blinding

This is an open-label study.

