## **6.11. Concomitant Medications and Non-Drug Therapies**

Concomitant medications, including over-the-counter medications and supplements, taken during the study will be recorded in the eCRF. Drug names and start/stop dates will be recorded for general concomitant medications, while additional details, including dose, route of administration, and dosing frequency, will be recorded for certain medications (e.g., ESAs, iron, anti-hypertensive medications). Further details are provided in the SRM.

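### The only stated anti-hypertensive summary counts a change only if raised blood pressure was its cause; in an open-label study an all-reasons count of intensification by arm should stand beside it

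*Protocol*

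**What the plan says.** Protocol Section 9.4.4.3 (Other Safety Parameters) tabulates subjects with "any change in anti-hypertensive medications (type and/or dose) due to increased blood pressure will be tabulated". The same paragraph sends the criteria for potential clinical importance to the Reporting and Analysis Plan (RAP), but it states this counting rule itself.

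Section 6.11 lists what is collected. Drug names and start and stop dates are recorded for concomitant medications generally, and "additional details, including dose, route of administration, and dosing frequency, will be recorded for certain medications (e.g., ESAs, iron, anti-hypertensive medications") as well. A reason for change is not in that list, although the section leaves further details to the Study Reference Manual.

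Section 6.5 states: "This is an open-label study". The defence of that choice in Section 4.4 is that "it is unlikely that the open-label design will create any bias in the primary evaluation".

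Measured blood pressure is also collected and analysed. Section 7.4.5 says "One reading of blood pressure and pulse rate will be taken and recorded in the source document and the CRF". Section 9.4.4.3 adds "For laboratory tests, vital signs and ECG, parameters and/or changes from baseline will be summarized using summary statistics at each assessment visit" and "The number and percentage of subjects with values of the potential clinical importance values will be tabulated". Section 9.4.4 frames all of this as descriptive: "safety data will be summarized by each cohort and each treatment group in the Safety Population".

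**The concern.** A safety count that depends on why a drug was changed is only as comparable between arms as the assignment of the reason. In an open-label study that reason is probably given with the arm known. Section 4.6.2 suggests that ESA exposure may carry a cardiovascular risk that GSK1278863 may avoid, so sites may have a directional expectation. If raised blood pressure is cited more readily in one arm, the table shows a difference that the drug changes do not. A real difference could be hidden in the same way.

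The count also combines any change in type or dose. A one-for-one switch counts the same as an added agent or a higher dose, although the latter two say more about blood pressure that has become harder to control.

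This matters because a rise that is treated may not appear in the visit means, which come from one reading per assessment taken while the extra treatment is acting. Hypertension is not on the list of adverse events of special interest (Section 7.4.2) or the cardiovascular event list (Section 12.6.3). The anti-hypertensive count is therefore a useful complement to measured pressure, and an unfiltered form of it is not planned.

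**Working it through.** The plan gives no figure on this point, so there is none to reproduce. The check has two parts.

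**1. The text, set side by side.**

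- Counting rule (9.4.4.3): change in type and/or dose, and cause is raised blood pressure.
- Who assigns the cause, and how: not stated in the protocol.
- Blinding (6.5): none.
- Scope of the no-bias argument (4.4): the primary evaluation only. It rests on Hgb being an objective measure and on a prespecified dose algorithm. Neither bears on why an anti-hypertensive was changed.
- Data available (6.11): drug, dates, dose, route, frequency. These are enough to identify added agents, dose increases and substitutions without using a reason.

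So the cause filter is fixed in the protocol, it is exposed to knowledge of the arm, and a count that does not need it can be made from data already planned.

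**2. How far differential attribution could move the table.** The only input from the documents is 135 per arm (Section 4.3); the Safety Population could be slightly smaller. The rates are assumptions. Let *t* be the true proportion with a change, equal in both arms, and *a* and *b* the proportions of those changes attributed to raised blood pressure in the two arms.

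- Tabulated proportions: p1 = t × a and p2 = t × b
- Spurious difference: t × (a − b)
- 95% half-width: 1.96 × √[p1(1 − p1)/135 + p2(1 − p2)/135]

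Worked case, t = 0.30, a = 0.90, b = 0.60: p1 = 0.27, p2 = 0.18, difference 0.09. Half-width = 1.96 × √[(0.1971 + 0.1476)/135] = 1.96 × 0.0505 = 0.099.

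| t | a against b | p1 against p2 | Spurious difference (points) | 95% half-width (points) |
|---|---|---|---|---|
| 20% | 90% / 90% | 18% / 18% | 0 | 9.2 |
| 20% | 90% / 80% | 18% / 16% | 2 | 9.0 |
| 20% | 90% / 60% | 18% / 12% | 6 | 8.5 |
| 30% | 90% / 90% | 27% / 27% | 0 | 10.6 |
| 30% | 90% / 80% | 27% / 24% | 3 | 10.4 |
| 30% | 90% / 60% | 27% / 18% | 9 | 9.9 |
| 40% | 90% / 90% | 36% / 36% | 0 | 11.5 |
| 40% | 90% / 80% | 36% / 32% | 4 | 11.3 |
| 40% | 90% / 60% | 36% / 24% | 12 | 10.8 |

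A second set of assumed rates gives the same order of size: at t = 0.30, 80% against 60% gives 24% against 18%, a 6-point difference, or 0.06 × 135 = 8.1 subjects. The artefact is zero when a = b. It reaches the size of the sampling error only when the two arms differ widely in attribution.

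**The case against.** The case against has real weight.

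- **No assigner is named.** A reader might infer that an unblinded investigator decides each case. The protocol does not say so. The cause could be derived from a recorded indication or a blood-pressure rule, and the RAP or the Study Reference Manual could define it. The absence of that definition is not itself a fault in a protocol. What stands is that the protocol fixes a cause-filtered count and no unfiltered one. A site attribution is the natural reading, not a certainty.
- **It is not the main blood-pressure comparison.** A reader might infer that it is, but nothing ranks it so. Visit summaries and threshold counts of vital signs sit in the same section and do not use the filter, and adverse events are tabulated separately. This point stands, and it limits the finding to one descriptive table.
- **Opinion does not replace the drug record.** A change in type or dose is still required; the cause is an added condition. This point stands too.
- **The filter has a purpose.** It targets changes made because of blood pressure, and dropping it admits changes made for other reasons. That is a reason to report both counts, not to report only the filtered one.
- **Prescribing is also unblinded.** The same sites decide whether to add a drug or raise a dose. Counting all intensifications removes differential attribution but not differential prescribing. A careless definition of a new agent would also count plain substitutions, so these need a separate row.

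**Conclusion.** The point holds in a limited form. The protocol's only stated anti-hypertensive summary makes a descriptive between-arm safety count depend on a cause that is probably assigned with knowledge of the arm, and it does not separate intensification from other changes. The protocol's own argument against open-label bias does not reach this table.

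The size of any bias is unknown. The 2 to 12 points shown above rest wholly on assumed change and attribution rates, and the direction could be either way. The documents do not support a claim that bias will occur, that the blood-pressure assessment as a whole depends on opinion, or that the primary or principal secondary conclusion is affected. This is a worthwhile, low-cost improvement to one safety table.

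**What to change.** In Section 9.4.4.3, and in the RAP to match, add for Cohort 1 a tabulation by arm, in the Safety Population, of:

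- the number (%) of subjects with anti-hypertensive intensification after Day 1, whatever the reason, defined as an agent added without a concurrent stop of another, or a dose increase of an existing agent;
- the number (%) with one-for-one substitutions, shown separately;
- the existing cause-filtered count, kept as a labelled subset of the recorded changes, with a statement of who assigns the cause and by what rule.

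A between-arm difference with a 95% CI for the first row is optional.

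The cost is analysis wording and a few table rows, since Section 6.11 already provides for drug, dates and dose. It needs no new data and changes nothing in how subjects are treated. The downsides are that changes made for other reasons add noise in both arms, and that unblinded prescribing decisions are not corrected.
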